**NCT Number:**

## **Efficacy Of Nasal Irrigation With Combination of 0.9% NaCl and Binahong Extract (*Anredera Cordifolia*) 2,5% In Allergic Rhinitis**

### **Background**

The current management of RA includes education, reducing exposure to allergens, pharmacology, immunotherapy, and complementary (Linton et al., 2021). Clinical practice therapy guidelines were developed on Allergic Rhinitis and its Impact on Asthma (ARIA) through integrated social media, mobile health, and multidisciplinary services (Bousquet et al., 2019; Zhang et al., 2021). According to ARIA recommendations, therapy aims to control the symptoms that arise. However, 20% more patients are still symptomatic even though they have received adequate therapy according to treatment guidelines. To overcome this problem, in the 20th century, personalized medicine developed a therapeutic method that adapts individual patient characteristics with a genetic basis, immunology, and bio-psycho-social profiles as a dynamic process (Licari et al., 2019). This therapeutic approach aims to minimize side effects, increase therapeutic success, and develop into precision medicine. The target of therapy that is currently being developed is to modify the immune response to allergens and prevent disease development with a preventive approach, namely at the beginning of the process when the allergen attaches to the nasal mucosa (Agache & Akdis, 2019; Dubey et al., 2019).

A study of the 0.3% Binahong extract combination, which has an anti-inflammatory effect on 0.9% NaCl nasal wash therapy in adult allergic rhinitis patients, has never been done before. There is a potential role, together with physical and immunological mechanisms, to increase the efficacy of nasal washing. Based on the explanation above, it is necessary to research to determine the effect of a combination of 3% Binahong extract as a herbal medicine to increase the results of 0.9% NaCl nasal wash by assessing mRNA expression (IL-4, IL-6, IL-13, and TNF- $\alpha$ ) as the primary outcome. Besides that, secondary outcome assessments are still carried out in clinical symptoms, quality of life, and nasal physiology, which researchers usually do to assess treatment in allergic rhinitis patients. Hopefully, this research will become a source of allergic rhinitis therapy and support the independence of drugs with natural ingredients.

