## Methods

This study was designed with the Consolidated Standards of Reporting Trials (CONSORT) guidelines by clearly stating the items that must be informed in RCT research reports to avoid bias. The research flow process will follow the flowchart guidelines of the enrollment, allocation, follow-up, and analysis phases (Schulz et al., 2011). This research is a quantitative experimental study with a single-blind parallel randomized controlled trial design to determine the results of intervention for 0.9% NaCl nasal irrigation therapy added with 3% Binahong extract compared to the control group 0.9% NaCl nasal irrigation therapy for two weeks in adult RA sufferers, which are schematically described as follows:

[figure not shown]

Figure 1. Research Design

Information:

P = Population

S = Sample

R = randomization of allocations

O1 = Examination before treatment

O2 = Examination before treatment

O3 = Examination after treatment

O4 = Examination after treatment

K = NaCl 0.9% nasal irrigation control

P = 0.9% NaCl nasal irrigation + 3% Binahong Extract

The process of randomization to allocate participants to the intervention group or control group was carried out using random numbers generated by a computer program and statistical software with an allocation of 1:1. The random number results were entered into sealed envelopes using the SNOSE (sequentially numbered, opaque sealed envelopes) system. Participants were assigned to the intervention or control group based on the order of randomization (allocation concealment) carried out by the research assistant and given a 0.9% NaCl nose irrigation pack plus 3% Binahong extract (freeze drying) or a 0.9% NaCl nose irrigation pack for two weeks. The investigators needed access to the blinding group's sequences, and the entire study team was instructed not to communicate with participants about their sequences.

The research sample was RA patients at the AMC Muhammadiyah General Hospital Polyclinic and PKU Muhammadiyah Gamping Hospital Yogyakarta who met the inclusion and exclusion criteria as follows:

1. Inclusion criteria
  - a. Patients with RA symptoms (SFAR score  $\geq 7$ ) (Widuri A, 2021), adult age (18 to 65 years), male or female
  - b. SPT examination results are positive
  - c. Agree to participate in the research (informed consent) in writing
2. Exclusion criteria
  - a. Pregnant or breastfeeding women
  - b. Active smoker
  - c. Local allergic rhinitis

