  - d. Patients with autoimmune diseases
  - e. Chronic rhinosinusitis with or without nasal polyps

The number of samples in this study was determined using the sample size formula for research that aims to determine the change in the average (mean) before and after the intervention of the two paired groups tested with paired t-test. The variables to be examined in this study are:

1. Independent variable: nasal washing treatment with 0.9% NaCl + 3% concentration of Binahong Extract or control nasal washing with 0.9% NaCl.

NCT Number:  
13 March 2023

2. Dependent variables: mRNA expression (IL-4, IL-6, IL-13, and TNF- $\alpha$ ), SNOT-22, Mini-RQLQ, Nasal flow and Patency, and Mucociliary Transport Time.
3. Control variables: gender, classification.

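### Optional improvement: add the baseline value of the same outcome to the control variables and use it as a covariate when the arms are compared

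*Protocol*

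**What the plan says.** All of the relevant text is in the protocol's Methods section.

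- **Design.** The trial is a "single-blind parallel randomized controlled trial design". The extract-plus-saline arm is "compared to the control group 0.9% NaCl nasal irrigation therapy for two weeks", and patients are randomised "with an allocation of 1:1".
- **Timing of measurements.** The legend to Figure 1 includes "O1 = Examination before treatment" and "O3 = Examination after treatment", so outcomes are examined on both sides of the treatment period.
- **Test named.** The sample-size sentence refers to the "change in the average (mean) before and after the intervention of the two paired groups tested with paired t-test". No other test or model appears.
- **Control variables.** Item 3 of the list of variables reads "Control variables: gender, classification". The protocol does not say what these variables are used for, and it does not define classification.

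The primary outcome, given in the Background, is the expression of four cytokine mRNAs. Symptom, quality-of-life and nasal-function measures are secondary.

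**The concern.** The trial's question is whether one arm does better than the other. For that comparison the protocol lists two general patient characteristics as control variables. It leaves out the patient's own starting value, which is often the strongest single predictor of the value two weeks later.

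The protocol does not state how the arms will be compared. Two simple choices are open. A comparison of changes from baseline fixes the slope of follow-up on baseline at 1. This is optimal only when the correlation times the ratio of post- to pre-treatment SD equals 1. A comparison of final values fixes the slope at 0, which is optimal only when baseline carries no information. ANCOVA estimates the slope from the data and usually does better than both.

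Only precision is at stake: a wider confidence interval, or more patients for the same power, than the collected data require.

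**Working it through.** **Inputs.** The protocol states no N, SD, effect size, power or correlation, so it has no figure to reproduce. Every number below rests on assumptions: baseline/follow-up correlation r = 0.3, 0.5 or 0.7; equal SDs before and after treatment unless stated; total N of 30 or 60.

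**1. Variance of the arm difference before any cost.** Relative to a final-value comparison (= 1), a change score has variance 2(1 − r) and ANCOVA has 1 − r². Hence ANCOVA relative to a change score is (1 − r²)/[2(1 − r)] = (1 + r)/2.

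| r | ANCOVA / change score | ANCOVA / final value |
|---|---|---|
| 0.3 | 0.65 | 0.91 |
| 0.5 | 0.75 | 0.75 |
| 0.7 | 0.85 | 0.51 |

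**2. Cost of estimating the slope.** With baseline as the only covariate, the variance is inflated on average by 1 + 1/(N − 4).

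- N = 30: 1 + 1/26 = 1.038
- N = 60: 1 + 1/56 = 1.018

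If gender and a two-level classification were also in the model, the factor would be 1 + 1/(N − 6), that is 1.042 and 1.019. Rounded, the cost is 4% and 2% either way.

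**3. Net of that cost (baseline as the only covariate).**

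| N | r | vs change score | vs final value |
|---|---|---|---|
| 30 | 0.3 | 0.675 | 0.945 |
| 30 | 0.5 | 0.779 | 0.779 |
| 30 | 0.7 | 0.883 | 0.530 |
| 60 | 0.3 | 0.662 | 0.926 |
| 60 | 0.5 | 0.763 | 0.763 |
| 60 | 0.7 | 0.865 | 0.519 |

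**4. Where the gain disappears against a final-value comparison.** Setting (1 − r²)[1 + 1/(N − 4)] = 1 gives r = √[1/(N − 3)].

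- N = 30: √(1/27) = 0.19
- N = 60: √(1/57) = 0.13

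Below these values ANCOVA loses slightly.

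**5. If other covariates are already in the model.** The r that counts is then the partial correlation given those covariates. Suppose classification correlates 0.5 with both baseline and follow-up. A raw r of 0.3 becomes (0.3 − 0.25)/(1 − 0.25) = 0.067. The ratio to a final-value comparison is 1 − 0.067² = 0.996, and at N = 30 this becomes 0.996 × 1.042 = 1.04, a loss of about 4%. A simulation of 20,000 trials under these assumptions gave 1.04 as well.

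**6. Unequal SDs.** With k = post SD / pre SD, ANCOVA relative to a change score is k²(1 − r²)/(1 + k² − 2rk). At k = 1.25 and r = 0.7 this is 0.797/0.8125 = 0.98. After the slope cost at N = 30 it is 0.98 × 1.038 = 1.02. Here the fixed slope of 1 is already close to the best slope, 0.7 × 1.25 = 0.875, so little is left to gain.

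**7. In patients.** For a standardised difference of 0.5, two-sided 5% significance and 80% power (all assumed), a final-value comparison needs 63 per arm. ANCOVA needs 58, 48 or 33 at r = 0.3, 0.5 or 0.7, and a change score needs 88, 63 or 38. These counts leave out the slope cost.

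**The case against.** The strongest case against the point is one of scope. The covariates of a between-arm model are ordinarily settled in the SAP, which is not shown here. The protocol's list sorts the study's variables into independent, dependent and control, and it is attached to no model. A baseline outcome is the dependent variable measured early, so its absence from the control heading does not show that it will be left out of the analysis. The sample-size sentence speaks of before/after change. If the arms are compared on change, baseline already enters with a fixed slope.

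Most of this stands, and it limits the point to an option. It does not remove it, because the protocol wrote its own list of control variables and named a test, and neither uses baseline as a covariate in the between-arm comparison.

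A reader might draw three stronger inferences that the document does not support.

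- **That the omission biases the result.** It does not: under randomisation, final-value, change-score and baseline-adjusted comparisons all estimate the arm difference without bias from this source.
- **That the trial will be judged by paired tests within each arm.** The paired t-test is named only as the basis of the sample size. Whether that basis suits a parallel design is a separate question.
- **That adjustment is certain to help.** Steps 4 to 6 above show settings where the gain is nil or slightly negative. No correlation is given for the mRNA outcomes, so they cannot be assumed to lie in the favourable range.

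**Conclusion.** The point holds as an optional, inexpensive improvement. The protocol's control variables omit the baseline value of the outcome, and the only test it names does not compare the arms. Baseline-adjusted ANCOVA is a better-defined between-arm analysis than anything the text states, and it is usually more precise.

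The size is conditional. Before the slope cost, and with equal SDs and a correlation of 0.3 to 0.7, the variance falls by 15% to 35% against a change score and by 9% to 49% against final values. A small loss is possible at low correlation in a small trial. The conclusion also rests on reading the control variables as intended covariates, which is an inference, and on baseline values being collected as the before/after examinations imply. If the SAP already adjusts for baseline, all that remains is to bring item 3 into line with it.

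**What to change.** Unless the SAP already does so, add *baseline value of the same outcome* to item 3 of the list of variables. Then state that, for each outcome, the arms are compared by ANCOVA of the post-treatment value on arm, with the baseline value of that outcome as a covariate. Baseline and follow-up should be on the same scale.

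The argument supports only this one added term. It does not require gender or classification to be made covariates for every outcome, least of all while classification is undefined. It also does not settle whether mRNA expression should be transformed. Both choices can be left to the SAP.

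The cost is one or two lines of text, a standard model, and one degree of freedom per outcome. No new data are needed if the pre-treatment examinations cover every outcome. The remaining downside is the slight loss of precision that is possible in a small trial with a weak baseline correlation.
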